3.2.9 Safety evaluation

All safety analyses will be performed based on the Safety Set.

Grouping for the analyses

Safety summaries will include data from the following three mutually exclusive segments:

- Pre-treatment period: from day of patient's informed consent to the day before first dose of study treatment.
- On-treatment period:
 - For discontinued patients, from day of first dose of study drug to 30 days after last dose of study drug
 - For ongoing patients, from day of first dose of study drug to the data cut-off date
- Post-treatment period: starting at day 31 after last dose of study drug

The safety summary tables will include only assessments during the on-treatment period, unless otherwise specified. For select items, shift tables or change from baseline summaries generated

for laboratory, ECG, vital signs and change score generation may use data from pre-treatment period for baseline calculations.

All data, regardless of observation period, will be listed and assessments collected in pre-treatment and post-treatment period will be flagged in all the listings.

3.2.9.1 Adverse events (AEs)

Summary tables for AEs will include only AEs observed during the on-treatment period. AEs will be coded using MedDRA using the latest version available prior to clinical database lock and will be graded using Common Terminology Criteria for Adverse Events (CTCAE) version 4.03. If CTCAE grading does not exist for an AE, grades 1, 2, 3, or 4 corresponding to the severity of mild, moderate, severe, and life-threatening, respectively, will be used. CTCAE grade 5 (death) will not be used in this study; rather, this information will be collected on the “End of Treatment Phase Disposition”, “Post-treatment Phase Completion” or “Death” eCRF pages.

All AE summaries will be summarized (frequency counts and percentages) by SOC and/or PT, maximum severity grades (based on CTCAE grades), and relation to study drug except where otherwise noted. A patient with multiple CTC grades for an AE will be summarized under the maximum CTC grade recorded for the event.

Deaths reportable as SAEs and non-fatal SAEs will be listed by patient. AEs leading to study discontinuation and AEs requiring dose adjustment or interruption will be listed separately.

The following AE summaries will be produced:

- AEs regardless of study drug relationship
- AEs suspected to be study drug related
- All deaths, by primary SOC and PT
- On-treatment deaths, by primary SOC and PT
- SAEs regardless of study drug relationship
- SAEs suspected to be study drug related
- AEs associated with discontinuation of study drug
- AEs requiring dose adjustment or study drug interruption
- AEs requiring dose adjustment
- AEs requiring study drug interruption
- AEs requiring concomitant medication or non-drug therapy
- AEs excluding SAEs
- On-treatment deaths and serious adverse events by primary SOC and PT
- Non-serious adverse events (threshold = 5%) by primary SOC and PT

Adverse events of special interest

AESIs are defined as AEs within the following categories/ groupings of PTs:

- Hepatotoxicity
- Interstitial lung disease/Pneumonitis

CONFIDENTIAL - For Business Use Only

- QTc prolongation
- Hyperglycemia
- Bradycardia
- GI toxicity (including nausea, diarrhea, vomiting)
- Pancreatitis (including lipase or amylase increases)

AESIs are also referred to as clinically notable adverse events (CNAEs) in the protocol. CNAEs are defined at the project level and may be updated based on emergent data to reflect new CNAEs of interest at the time of analysis. The CNAEs listed above will be identified based on a list of PTs. Both the final categories of AESI and the list of preferred terms should refer to the Case Retrieval Strategy at the time of database lock, which will be finalized in a separate document. These CNAEs will be summarized for each grouping, by PT, as follows:

- All CNAEs
- CTC grade 3/4 CNAEs
- CNAEs suspected to be study drug related
- Serious CNAEs
- CNAEs leading to study drug discontinuation
- CNAEs requiring dose adjustment or study drug interruption.
- CNAEs requiring dose adjustment
- CNAEs requiring study drug interruption

3.2.9.2 Laboratory data

For laboratory data assessments, data from all sources (central and local laboratories) will be combined. The summaries will include all laboratory assessments collected no later than 30 days after study drug discontinuation. All laboratory assessments will be listed and those collected in post-treatment period will be flagged in the listings.

Laboratory data will be classified (by Novartis Oncology Statistical programming) into CTC grades according to the NCI CTCAE v4.03. For all reports, CTC grade is always obtained on the converted measurement in SI unit. The CTC grade 0 will be assigned as below in different scenarios:

- For lab parameters defined by criteria based on normal range only, a severity grade of 0 will be assigned when the value is within normal limits.
- For lab parameters whose grade is defined by criteria based on normal range and absolute values (e.g. platelet count decrease). A severity grade of 0 will be assigned when the value is within normal limits.
- For lab parameters whose grade is defined by criteria based on normal range and the change from baseline value, with no other associated clinical criteria such as concomitant medication (e.g. creatinine increased), the following will be applied. For the baseline grading and for the grading of post-baseline lab values with missing baseline grading, the grade will be derived using the criteria based only on the normal range as per CTCAE v4.03.

A severity grade of 0 will be assigned when the post-baseline value is \leq ULN (for hyper) or \geq LLN (for hypo).

- For CTC grades of glucose (fasting or non-fasting), glucose fasting values will be used. For glucose non-fasting values, Grade 1 or 2 will be reassigned to Grade 0.

Grade 5 will not be used. Parameters for which a grading does not exist will be classified into low/normal/high group by means of laboratory normal ranges.

The following summaries will be produced for the hematology and biochemistry laboratory data (by laboratory parameter):

- Shift tables using CTC grades to compare baseline to the worst post-baseline value for laboratory parameters with CTC grades
- Shift tables using low, normal, high (as well as low and high combined) classifications to compare baseline to the worst post-baseline value for laboratory parameters where CTC grades are not defined.

The following lab parameters will be summarized:

- Hematology: absolute lymphocytes, absolute neutrophils, hemoglobin (anemia), white blood cell (WBC), platelet counts, absolute basophils, absolute eosinophils, absolute monocytes, red blood cells(RBC)
- Biochemistry: alkaline phosphatase (ALP), alanine aminotransferase (ALT), aspartate aminotransferase (AST), total bilirubin, amylase, potassium, sodium, creatinine, glucose(fasting), phosphate, albumin, calcium (corrected for albumin), magnesium, creatinine clearance, direct bilirubin, blood urea nitrogen (BUN) or urea, lipase, Gamma glutamyl transferase (GGT)

For bi-directional parameters, both hyper and hypo summaries will be presented.

- Hormones (males only): Testosterone, LH, FSH, sex hormone binding globulin (SHBG).

In addition, for hematology and biochemistry parameters, a summary table with frequency counts and percentages of patients of new and worsen abnormalities based on CTC grade will be presented.

The following laboratory parameters will be presented in listings and will not be summarized:

- Urinalysis: macroscopic panel (dipstick) (bilirubin, blood, glucose, ketones, WBC, nitrite, pH, protein, specific gravity, urobilinogen), Urinalysis Microscopic panel (RBC, WBC, casts, crystals, bacteria, epithelial cells).
- Coagulation: INR, pro-thrombin time (PT) or Quick Test

The following listings will be produced for the laboratory data for all laboratory parameters where CTC grades are defined:

- Listing of patients with laboratory abnormalities of CTC grade 3 or 4
- Listing of all laboratory data with values flagged to show the corresponding CTC grades and the classifications relative to the laboratory reference ranges.

Liver function tests (LFTs) of interest for LDK378 are total bilirubin (TBIL), ALT, AST and ALP. In what follows, AT refers to ALT or AST values. LFTs will be summarized as follows:

- Shift tables of baseline vs. worst post-baseline on-treatment values for the categories:

- $\text{TBILI} \leq 2 \times \text{ULN}$, $\text{TBILI} > 2 \times \text{ULN}$ and missing TBILI
- $\text{ALT} \leq 3 \times \text{ULN}$, $\text{ALT} > 3 \times \text{ULN}$ and missing ALT
- $\text{AST} \leq 3 \times \text{ULN}$, $\text{AST} > 3 \times \text{ULN}$ and missing AST
- $\text{ALP} < 2 \times \text{ULN}$, $\text{ALP} \geq 2 \times \text{ULN}$ and missing ALP
- Frequency counts and percentages of patients with worst post-baseline on-treatment values in the categories:
 - $\text{ALT} > 3 \times \text{ULN}$, $\text{ALT} > 5 \times \text{ULN}$, $\text{ALT} > 10 \times \text{ULN}$, $\text{ALT} > 20 \times \text{ULN}$
 - $\text{AST} > 3 \times \text{ULN}$, $\text{AST} > 5 \times \text{ULN}$, $\text{AST} > 10 \times \text{ULN}$, $\text{AST} > 20 \times \text{ULN}$
 - $\text{AT} > 3 \times \text{ULN}$, $\text{AT} > 5 \times \text{ULN}$, $\text{AT} > 10 \times \text{ULN}$, $\text{AT} > 20 \times \text{ULN}$
 - $\text{TBILI} > 2 \times \text{ULN}$
 - Concurrent $\text{ALT} > 3 \times \text{ULN}$ and $\text{TBILI} > 2 \times \text{ULN}$
 - Concurrent $\text{AST} > 3 \times \text{ULN}$ and $\text{TBILI} > 2 \times \text{ULN}$
 - Concurrent $\text{AT} > 3 \times \text{ULN}$ and $\text{TBILI} > 2 \times \text{ULN}$
 - Concurrent $\text{AT} > 3 \times \text{ULN}$ and $\text{TBILI} > 2 \times \text{ULN}$ and $\text{ALP} < 2 \times \text{ULN}$
 - Concurrent $\text{AT} > 3 \times \text{ULN}$ and $\text{TBILI} > 2 \times \text{ULN}$ and $\text{ALP} \geq 2 \times \text{ULN}$

Concurrent measurements are those occurring on the same date.

In addition, a listing of all TBILI , ALT , AST and ALP values for patients with a post-baseline $\text{TBILI} > 2 \times \text{ULN}$, $\text{ALT} > 3 \times \text{ULN}$ or $\text{AST} > 3 \times \text{ULN}$ will be provided.

3.2.9.3 ECGs

ECG data will be analysed based on central reading. The summaries will include all ECG assessments performed no later than 30 days after the last date of study drug. All ECG assessments will be listed, and those collected later than 30 days after study drug discontinuation will be flagged in the listing.

Selecting Primary QT Correction for Heart Rate

The analysis of QT data is complicated by the fact that the QT interval is highly correlated with heart rate. Because of this correlation, formulas are routinely used to obtain a corrected value, denoted QTc , which is independent of heart rate. This QTc interval is intended to represent the QT interval at a standardized heart rate. Several correction formulas have been proposed in the literature. For this analysis we will use some of those methods of correction, as described below. The QT interval corrected for heart rate by the Bazett's formula, QTcB , is defined as

$$\text{QTcB} = \frac{QT}{\sqrt{RR}},$$

the QT interval corrected for heart rate by the Fridericia's formula, QTcF , is defined as

$$\text{QTcF} = \frac{QT}{\sqrt[3]{RR}}$$

where RR represents the RR interval of the ECG, in seconds.

Although Bazett's correction is the historical standard, it does not perform well when heart rate fluctuates. Fridericia's formula may perform better under these conditions. An alternate correction to achieve the goal of getting uncorrelated QTc and RR is based on linear or log-linear regression methods which yield, theoretically, uncorrelated QTc and RR.

Linear regression method:

- Fit a model $QT = a + b * RR$ to baseline data
- Use the estimated slope, \hat{b} , to correct QT
- Corrected QT for heart rate will be computed as follows:

$$QTcP = QT + \hat{b} * (1 - RR)$$

Log-linear regression method:

- Fit a model $Log_e(QT) = a + b * Log_e(RR)$ to baseline data
- Use the estimated slope, \hat{b} , to correct QT
- Corrected QT for heart rate will be computed as follows:

$$QTcLogP = \frac{QT}{RR^{\hat{b}}}$$

Data will be summarized using QTcF and QTcB. However, if these are not appropriate for the data set due to an observed large correlation between corrected QT and HR using the baseline assessments, the results will also be summarized using one of QTcP or QTcLogP.

ECG Summaries

The following analyses will be performed for each applicable ECG parameters (RR, PR, QRS, QT, ventricular rate -denoted as HR in what follows-, and QTc) as noted.

- Pearson correlation between QT and RR, QTc (QTcB, QTcF and, if applicable, one of QTcP or QTcLogP) and RR using individual (non-averaged) baseline assessments and separately using on-treatment assessments
- For each of the ECG parameters (HR, and QT, QTc, QRS, PR intervals), descriptive statistics at baseline, at each post-baseline time point and changes from baseline at each post-baseline time point
- For each of the QTc and QT intervals, shift tables based on notable parameter categories (≤ 450 , $> 450 - \leq 480$, $> 480 - \leq 500$, > 500 ms) at baseline and the worst post-baseline value observed
- Frequency counts and percentages of patients having notable ECG values according to the following categories:
 - QT parameter (QT, QTc) increase from baseline > 30 ms, > 60 ms
 - Newly occurring post-baseline QT parameter > 450 ms, > 480 ms, > 500 ms
 - HR increase from baseline $> 25\%$ and value > 100 bpm
 - HR decrease from baseline $> 25\%$ and value < 50 bpm
 - PR increase from baseline $> 25\%$ and value > 200 ms

- Newly occurring post-baseline PR > 200 ms and \leq 220 ms, > 220 ms
- QRS increase from baseline > 25% and value > 110 ms
- Newly occurring post-baseline QRS > 110 ms and \leq 120 ms, > 120 ms

The denominator to calculate percentages for each category is the number of patients at risk for a specific category. For new abnormality post baseline, the denominator is the number of patients with both a baseline and a post-baseline evaluation and baseline not meeting the criterion. A newly occurring post-baseline ECG notable value is defined as a post-baseline value that meets the criterion post-baseline but did not meet the criterion at baseline

- Frequency counts and percentages of patients with newly occurring post-baseline qualitative ECG abnormalities (morphology) will be summarized. The denominator to calculate percentages for each individual finding is the number of patients with both a baseline and a post-baseline evaluation and baseline being normal, i.e. those patients who are at risk of developing this abnormality. A newly occurring post-baseline qualitative ECG abnormality is defined as a post-baseline abnormal finding which was not present at baseline.

Patients with notable ECG interval values and newly occurring qualitative ECG abnormalities will be listed by patient, time point, the corresponding notable values and abnormality findings.

Unscheduled ECG measurements will not be used in computing the descriptive statistics for change from baseline at each post-baseline time point. However, they will be used in the analysis of notable ECG changes and the shift table analysis of notable QT parameters.

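### Two closed-band ECG rows (PR above 200 to 220 ms, QRS above 110 to 120 ms) count shortening from a longer baseline as a newly occurring abnormality

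*SAP*

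**What the plan says.** SAP 3.2.9.3, under the ECG summaries, lists notable categories with counts and percentages. The newly occurring rows take two shapes.

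- **Open thresholds, QT and QTc:** "Newly occurring post-baseline QT parameter > 450 ms, > 480 ms, > 500 ms".
- **A closed band followed by an open threshold, PR and QRS:** "Newly occurring post-baseline PR > 200 ms and \leq 220 ms, > 220 ms" and "Newly occurring post-baseline QRS > 110 ms and \leq 120 ms, > 120 ms".

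On the denominator the section first says: "The denominator to calculate percentages for each category is the number of patients at risk for a specific category". It then makes this specific for new abnormalities: the patient must have a baseline and a post-baseline evaluation, and the baseline must not meet the criterion. The numerator is "a post-baseline value that meets the criterion post-baseline but did not meet the criterion at baseline". Neither sentence requires the later value to be worse than baseline.

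SAP 3.1.5.1 brings scheduled, unscheduled and repeat post-baseline values into any analysis of abnormal assessments. The end of SAP 3.2.9.3 confirms that unscheduled ECGs are used for notable changes.

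For qualitative (morphology) findings, the denominator for each individual finding is "the number of patients with both a baseline and a post-baseline evaluation and baseline being normal", glossed as those at risk of that abnormality. The numerator is "a post-baseline abnormal finding which was not present at baseline".

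**The concern.** For an open threshold, a patient whose baseline fails the criterion can meet it later only by getting worse. A closed band can be entered from either side. Someone starting above the upper limit fails the band criterion at baseline, is therefore treated as at risk, and meets it later by improving.

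ECGs are a named endpoint of the primary safety objective (Protocol Table 3-1 and 10.4.1.2). The table of notable ECG values is among the first interpretable results at both the interim and primary analyses (SAP 4.5.1 and 4.5.2). The study has a single arm and is meant to support registration, so no control group would show the same artefact.

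Patients of this kind can enrol. Protocol 5.3 sets a QTcF limit at screening but no PR or QRS limit. SAP 3.2.9.3 specifies shift tables by notable category for QT and QTc only. Protocol 10.5.3.4 asks for an ECG shift table without naming the intervals.

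**Working it through.** The documents give no figure for these rows, so there is nothing to reproduce. The check has three parts.

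**1. Apply the stated rule to every pair of categories.** A patient is counted as new if the row's criterion is met after baseline and was not met at baseline. Representative values were PR 190, 210, 230 ms; QRS 100, 115, 130 ms; QTc 440, 465, 490, 510 ms.

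| Row | Pairs counted as new (baseline to later) | Any improvement counted? |
|---|---|---|
| PR >200 to ≤220 | 190 to 210; 230 to 210 | Yes, 230 to 210 |
| PR >220 | 190 to 230; 210 to 230 | No |
| QRS >110 to ≤120 | 100 to 115; 130 to 115 | Yes, 130 to 115 |
| QRS >120 | 100 to 130; 115 to 130 | No |
| QTc >450, >480, >500 | upward moves only | No |

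Exactly two cells are wrong, one in each closed band. Classifying by worst post-baseline value does not remove them: baseline PR 230 ms with a worst later value of 215 ms still lands in the band.

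**2. Effect on a reported percentage.** N = 103 is the number treated (Protocol, amendment rationales). Everything else is assumed: 4 patients truly new from at or below 200 ms, *a* patients in the band at baseline, *b* above it, and every one of the *b* later counted in the band.

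- As written: (4 + b)/(103 − a).
- Corrected: 4/(103 − a − b).

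| a | b | As written | Corrected |
|---|---|---|---|
| 0 | 0 | 4/103 = 3.9% | 4/103 = 3.9% |
| 5 | 2 | 6/98 = 6.1% | 4/96 = 4.2% |
| 10 | 3 | 7/93 = 7.5% | 4/90 = 4.4% |
| 10 | 5 | 9/93 = 9.7% | 4/88 = 4.5% |

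**3. How easily a patient above the band falls into it.** Protocol Table 7-5 gives 15 post-baseline ECG time points through Cycle 6 plus end of treatment. Assume no drug effect and independent normal readings with mean m equal to baseline and SD s (both assumed). The chance that one PR reading is in the band is p = Φ((220 − m)/s) − Φ((200 − m)/s). If any value counts, the chance of being called new is 1 − (1 − p)^15.

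| m (ms) | s (ms) | p | Any of 15 |
|---|---|---|---|
| 222 | 5 | 0.345 | 0.998 |
| 222 | 8 | 0.398 | >0.999 |
| 225 | 5 | 0.159 | 0.925 |
| 225 | 8 | 0.265 | 0.990 |
| 230 | 5 | 0.023 | 0.292 |
| 230 | 8 | 0.106 | 0.812 |

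If patients are instead placed by worst value, all 15 readings must be at or below 220 ms. In the most favourable row (m = 222, s = 8) that is at most Φ(−0.25)^15 = 0.401^15, about 0.000001. Noise alone then contributes almost nothing, and only sustained shortening is miscounted.

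**The case against.** **Other outputs limit the damage.** The SAP also asks for PR and QRS change from baseline by time point, for directional rows (a rise of more than 25% together with a value above 200 or 110 ms), and for patient listings of notable values. A reader who checks these could spot a fall from 230 to 215 ms. This stands and limits the consequence, but it does not make the percentage in the row right.

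**The size depends on an unstated counting rule.** Including all post-baseline values does not settle whether a patient is counted on any value or on the worst one. The PR and QRS rows are mutually exclusive, unlike the nested QT rows, which fits a single placement by worst value. On that reading, random variation adds almost no false cases. This also stands: the high probabilities in the any-value table cannot be quoted as the expected effect. The defect in the rule itself remains under both readings.

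**The general at-risk sentence might be thought to rescue the bands.** It does not, because the next sentence defines at risk by the baseline criterion.

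**Qualitative findings.** A reader might infer that numerator and denominator are drawn from mismatched sets. That would follow if a normal baseline meant a wholly normal ECG. But the denominator is set finding by finding and explained as risk of that particular abnormality. This supports a reading in which the specific finding is absent at baseline, and the two parts then agree. It is an ambiguity, not an established error. The choice still matters. Suppose 3 new cases arise among normal baselines, 5 arise among patients with another baseline abnormality, and 10 to 40 of 103 have any baseline abnormality. The finding-specific rule gives 8/103 = 7.8%. A whole-ECG denominator gives 8/93 = 8.6% to 8/63 = 12.7%. Restricting the numerator as well gives 3/93 = 3.2% to 3/63 = 4.8%.

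**Conclusion.** The rule is wrong as written for the PR band above 200 to 220 ms and the QRS band above 110 to 120 ms. Followed literally, it reports a move from a longer interval into the band as a new abnormality.

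It would be tempting to conclude that the newly occurring ECG rules are wrong in general, or that the adverse events of special interest on QT prolongation and bradycardia are affected. The documents do not support either. The QT, PR above 220 ms and QRS above 120 ms rows define their at-risk sets correctly, and the heart-rate rows use directional change from baseline. The QTc shift tables, PK analyses and response rate are untouched.

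The consequence is a possibly inflated descriptive percentage in two rows. The illustration of about 6% to 10% reported against about 4% to 5% rests on assumed counts of new cases and of patients starting in or above the band, and on every patient above it later being counted. The number starting above it may be zero, in which case nothing changes. The repair is nevertheless worth making, because the rule is stated, fails on its own terms, and is cheap to correct.

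**What to change.** In SAP 3.2.9.3, for the two closed-band rows only:

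- Define at risk as a baseline PR of 200 ms or less, or a baseline QRS of 110 ms or less, with at least one post-baseline ECG.
- Draw the numerator from that same set.
- Place each patient once, by worst post-baseline value.

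Leave the PR above 220 ms, QRS above 120 ms and QT rows as they are.

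As a minor clarification, state that a normal baseline for qualitative findings means a baseline ECG is available and that specific finding is absent, and apply this to both numerator and denominator.

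The cost is a few lines of SAP text and a small program change. No new data are needed. If outputs already exist, the two rows can be rerun from the same dataset.
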